5.11. Period of Observation

For purposes of this study, the period of safety observation extends from the time of first dosing until the final evaluation during the study, including the 28-day follow-up safety visit. Short-term follow-up for patients who discontinue study therapy without documented progressive disease will continue every three months until the patient's disease worsens, until the patient begins subsequent anti-cancer treatment, or until the patient dies, whichever comes first.

5.12. Concomitant Medications and Procedures

All concomitant medications and supportive therapy taken within 4 weeks of Cycle 1, Day 1 and through 28 days after last study treatment must be recorded on the appropriate electronic case report form (eCRF). The identity of all medications, dosage, and route of administration, frequency, duration of administration, and indication for use will be recorded in the appropriate sections of the eCRF.

ImmunoGen, Inc. Confidential Page 77 of 138

5.12.1. Lubricating Artificial Tears

Patients will be required to use preservative-free, lubricating artificial tears on a daily basis, as directed by the product label or the treating physician (Section 5.8.3).

5.12.2. Corticosteroid Eye Drops

All patients enrolled in Cohort 5 will be required to self-administer corticosteroid eye drops (1% prednisolone; Pred Forte® or generic equivalent) during active study treatment (Section 5.8.2). Patients will record their eye drop administration in a patient diary, which will be entered on the CRF.

5.12.3. Antiemetic and antidiarrheal medications

Antiemetic (e.g. 5-HT₃ serotonin receptor antagonists such as palonosetron, granisetron or ondansetron) and antidiarrheal (e.g. loperamide) medications may be used at the discretion of the treating physician, but they are not to be used prophylactically.

5.12.4. Acetaminophen

All patients dosed according to Schedule B should receive 325-650 mg of acetaminophen (PO or IV) approximately 30 minutes prior to each infusion of IMGN853.

5.12.5. Folate-Containing Vitamins

Folate-containing vitamins are not to be taken during the course of the study.

5.12.6. Antineoplastic Therapy

Other chemotherapy, investigational agents, or biologic therapy will not be permitted during the study.

Palliative radiotherapy for local peripheral metastases not being used as target lesions is allowed. However, the need for such therapy may be an indication of disease progression and should be discussed with the Sponsor prior to implementation. Radiotherapy for central metastases (e.g. vertebral, meditational) will not be allowed; the need for such radiotherapy while on study will be seen as an indication of disease progression and the patient should be withdrawn from therapy.

5.12.7. Hematopoietic Growth Factors

Patients receiving recombinant erythropoietin or darbepoietin- α prior to study start may continue to receive pre-treatment doses.

The use of erythropoietic and granulocyte growth factors in accordance with ASCO guidelines may be implemented at the discretion of the treating physician after Cycle 1.

5.12.8. Anticoagulants

The use of low dose anticoagulants for maintenance of line patency is allowed. Thrombosis prophylaxis is allowed.

ImmunoGen, Inc. Confidential Page 78 of 138

5.12.9. Other Concomitant Medications

Medications for the treatment of adverse events or cancer symptoms (e.g. packed red blood cells and pain medications), are allowed. Prophylactic use of steroids and/or antihistamines will be considered if needed to alleviate mild-moderate infusion reactions. Additionally medications (not addressed above) used to treat underlying medical conditions at study entry including antiemetics and anti-diarrheals will be allowed to continue.

5.13. Overdose and Medication Error

Overdose – There is no known treatment/antidote available for IMGN853. Supportive measures should be instituted if an instance arises in which a patient suffers an overdose of study drug.

Medication Error – The Sponsor must be immediately notified in the event of error in prescribing, dispensing, administering and/or use of IMGN853, and the event must be reported on the eCRF.

ImmunoGen, Inc. Confidential Page 79 of 138

6. PHARMACOKINETIC (PK ASSESSMENTS)

6.1. Overview

Serial analyses of patient plasma will be performed to define the PK properties of IMGN853 when administered intravenously once every 3 weeks. Plasma will be analyzed for levels of IMGN853, free DM4, and total M9346A antibody to assess IMGN853 stability.

6.2. PK Schedule

6.2.1. Schedule A

Blood samples for PK measurements will be taken in Cycles 1 and 3, at the following time points:

Day 1 – predose, and following completion of infusion at the following timepoints: 0-10 minutes, and 2, and 4 hours (± 10 minutes)

Day 2 – 24 hours after completion of infusion (± 2 hours)

Day 3 – 48 hours after completion of infusion (± 2 hours)

Day 4 or 5, Day 8 and Day 15 – a single blood sample will be drawn for PK (±24 hours)

Additionally, a single pre-dose sample will be collected before the IMGN853 infusion and following completion of the infusion in Cycles 2, 4, 5 and 6. A single blood sample for analysis of HAHA and HADA will be taken on Day 1 of Cycles 2, 4, and 5 and at the End of Treatment and Follow-up visits.

The sample for HAHA and HADA analysis will be taken from the PK tube; no additional blood draw is necessary.

6.2.2. Schedule B

Blood samples for PK measurements will be taken in at the following time points:

Cycle 1 & 3:

Day 1 – predose, and following completion of infusion at the following timepoints: 0-10 minutes, and 2 and 4 hours (± 10 minutes)

Day 2 – 24 hours after completion of infusion (± 2 hours)

Day 8 – predose and within 10 minutes of completion of the infusion

Day 15 – predose, and following completion of infusion at the following timepoints: 0-10 minutes, and 2 and 4 hours (± 10 minutes)

Day 16 – 24 hours after completion of infusion (± 2 hours)

Day 22 – a single blood sample will be drawn for PK (\pm 24 hours)

Additionally, a single pre-dose sample will be collected before the IMGN853 infusion and following completion of the infusion in Cycles 2, 4, 5 and 6. A single blood sample for analysis

ImmunoGen, Inc. Confidential Page 80 of 138

of HAHA and HADA will be taken on Day 1 of Cycles 2, 4, and 5 and at the End of Treatment and Follow-up visits.

The sample for HAHA and HADA analysis will be taken from the PK tube; no additional blood draw is necessary.

Details of sample preparation and shipping are provided in the Laboratory Manual.

6.2.3. Additional PK Samples

Any patient who experiences a Grade 2 or greater infusion reaction during the administration of IMGN853 will have blood drawn within 3 hours of the onset of the reaction and one week later for determination of drug concentration, antibodies to IMGN853 and factors that may be related to hypersensitivity reactions (see Section 5.8.6).

PK samples may also be obtained as feasible any time during the treatment period for assessment of study drug related SAEs if deemed appropriate by the Investigator and Sponsor.

6.3. Immunogenicity Assessments

To assess for potential immunogenicity against IMGN853 or DM4, plasma samples taken for PK assessment in cycles 1 through 6 will be taken as outlined in Sections 6.2.1 and 6.2.2, using the same tube that is used for the PK assessment. The study will evaluate the potential impact of immunogenicity on PK, Pd, safety, and efficacy of IMGN853 and total M9346A antibody. Specifically, clinical characteristics such as PK, safety and efficacy of immune positive patients will be compared to the immune negative population.

ImmunoGen, Inc. Confidential Page 81 of 138

7. TRANSLATIONAL RESEARCH STUDIES

Translational research studies will be performed to generate data that will demonstrate proof-of-mechanism and characterize pharmacodynamics and anti-tumor effects of IMGN853. In addition, several biomarkers, including FOLR1, will be evaluated as potential biomarkers of clinical response to IMGN853. These will help guide further clinical development of IMGN853.

7.1. Correlation between FOLR1 Expression and IMGN853 anti-tumor activity

FOLR1 expression varies with tumor histology, as reported in the literature and demonstrated in our pre-clinical studies (Sections 1.1 and Investigators' Brochure). Based on the hypothesis that tumors expressing higher levels of FOLR1 are more likely to be susceptible to anti-tumor activity of IMGN853, a threshold for FOLR1 expression was determined for each tumor histology studied in the expansion cohorts. This was done based on molecular epidemiology data generated in a number of patient samples representative of different tumor types, as well as pre-clinical efficacy data.

7.1.1. Evaluation of FOLR1 Expression in Tumor Tissue During Dose-Escalation and Dose Expansion

FOLR1 expression in tumors will be analyzed via IHC. All patients must submit archived tumor tissue, formalin-fixed, paraffin embedded (FFPE) slides for analysis of FOLR1 expression by IHC. For dose escalation, patients with tumors known to have high incidence of FOLR1 expression (serous and endometrioid ovarian cancer, serous and endometrioid endometrial cancer and NSCLC adenocarcinoma or BAC) may submit archived tumor tissue for retrospective analysis after enrollment. All other patients must submit archived tumor tissue for documentation of FOLR1 positivity by IHC prior to enrollment. Any level of FOLR1 expression (i.e., $\geq 1\%$ of tumor staining at $\geq 1+$ intensity) is acceptable for enrollment in the dose escalation portion of the study. If a patient does not have archival material available for analysis, the patient may alternatively undergo a biopsy to assess FOLR1 expression. The decision to biopsy will be made once patient eligibility has been determined and on the basis of tumor accessibility and patient safety.

Only patients with the required FOLR1 expression levels by IHC will be eligible to enroll in the dose expansion cohorts. If a patient wishes to enroll and does not have archival material available for analysis, he or she must undergo a biopsy to assess FOLR1 expression. In the ovarian cancer cohorts (Cohort #s 1 and 3) eligible patients must meet the minimum requirement of FOLR1 positivity by IHC (\geq 25% of tumor staining at \geq 2+ intensity), and in the uterine cancer and NSCLC cohorts, patients will be required to have an H score \geq 100 for FOLR1 expression in order to be eligible to enroll.

The tumor samples will be analyzed for folate receptor alpha (FOLR1) expression in the Companion Diagnostics Pharma Services CAP-accredited and CLIA-certified laboratory and Pathology Services at Ventana Medical Systems, Inc.

ImmunoGen, Inc. Confidential Page 82 of 138

IHC data will be used to define any potential associations between FOLR1 expression and clinical response.

7.2. Exploratory Biomarker Studies

Studies in tumor tissue and blood will be performed to explore potential markers of IMGN853 sensitivity and resistance. The sections below describe specific activities that are planned, but other additional biomarkers/biological pathways may be investigated based on emerging data.

7.2.1. Potential Markers of Drug Sensitivity

As IMGN853 targets proliferating cells, Ki67 IHC staining will be assessed as a marker of cell proliferation on fresh biopsy samples from patients in Expansion Cohort 3. Potential associations between Ki67 levels and clinical response will be examined.

IMGN853 retains the ADCC activity of the parental M9346A antibody. Fc γ R is the principle leukocyte receptor that mediates ADCC and Fc γ R polymorphisms modulate leukocyte ADCC activity. Therefore, all patients will be genotyped for Fc γ R alleles via PBMC analysis at screening. Potential associations between Fc γ R genotype and clinical response will be examined.

7.2.2. Potential Markers of Drug Resistance

Drug efflux transporters and p-glycoprotein (PgP) in particular play an important role in cancer cell resistance to cytotoxic agents, including microtubule-targeting agents. Therefore, PgP IHC staining will be assessed as a marker of drug resistance in archived tumor tissues for all patients and on fresh biopsy samples obtained from patients in the Expansion Cohorts. Potential associations between PgP levels and clinical response will be examined.

7.2.3. Folate Pathway Markers

Preclinical studies suggest that FOLR1 is upregulated in folate deficiency and downregulated following folate repletion (Zhu 2001, Sadasivan 2002). Because folate deficiency can enhance FOLR1 expression via a homocysteine-dependent upregulation of FOLR1 mRNA translation (Antony 2004), plasma total homocysteine levels will be assessed in all patients at baseline, during Cycle 2 and at the end of treatment visit. Increased homocysteine levels correlate with low serum and RBC folate levels and suggest folate deficiency. Vitamin B12 deficiency similarly elevates homocysteine levels and also elevates plasma methylmalonate (MMA) levels. Plasma MMA will therefore be analyzed in parallel with plasma total homocysteine to differentiate folate and B12 status. Potential associations between plasma total homocysteine/MMA, FOLR1 expression, and clinical response will be examined.

7.3. Pharmacodynamic (Pd) and Proof of Mechanism (POM) Analyses

7.3.1. Pd and PoM studies in Tumor Biopsies (EOC Expansion Cohort #3 Only)

For this, patients with biopsy-accessible tumors will undergo core tumor biopsy at baseline and at Cycle 2, Day 8 ± 3 days. The patient must sign consent to undergo the biopsy procedure. The decision to biopsy will be made once patient eligibility has been determined and on the basis of tumor accessibility and patient safety.

ImmunoGen, Inc. Confidential Page 83 of 138

Biomarkers to characterize mechanisms involved in the anti-tumor activity of IMGN853 will be evaluated.

Binding of IMGN853 to FOLR1 on the surface of tumor cells results in internalization of the folate receptor. Changes in FOLR1 expression levels will be examined via pre- and post-dose tumor biopsy samples. The presence of IMGN853 will also be detected in tumor cells using IHC methods directed at the maytansinoid payload of IMGN853 (using an anti-maytansinoid antibody). Changes in Ki67 and other markers describing anti-proliferative and/or apoptotic effect of IMGN853 may also be investigated.

8. STUDY PROCEDURES

8.1. Informed Consent

Each patient or legally authorized representative must provide written informed consent before any study-required procedures are conducted, unless those procedures are performed as part of the patient's standard care.

8.2. Inclusion and Exclusion Criteria

The inclusion and exclusion criteria will be assessed during screening (within 28 days prior to the first dose of any study drug on Cycle 1, Day 1). A patient is considered enrolled when administered the first dose of any study drug.

Procedures for completion of enrollment information, and requirements to communicate with the Sponsor about enrollment, are detailed in the Study Manual.

8.3. Confirmation of Disease Diagnosis

At screening, disease diagnosis, and current disease status will be confirmed from information in the source record.

8.4. Demographic/Medical History

The age, race, and gender of the patient are to be recorded during screening.

During the Screening period, a complete medical history will be compiled for each patient. The history will include the background and progress of the patient's primary malignancy and include a description of all prior therapies for the primary malignancy.

8.5. Physical Examination, Weight and Height

Physical examination, height (screening only) and weight must be performed as indicated in the Schedule of Clinical Assessments (Appendix A and Appendix B). A complete physical examination - including assessments of general appearance, skin, head (eyes, ears, nose, and throat), neck, lungs, heart, abdomen, back, lymph nodes, extremities, and neurological system - will be completed at screening and end of treatment. Directed physical examinations will be completed at additional time points as specified in the Schedule of Events and Section 10.

Weight will be measured at screening and at other times specified in the Schedule of Clinical Assessments (Appendix A and Appendix B).

ImmunoGen, Inc. Confidential Page 85 of 138

8.6. Vital Signs

Vital signs will be measured as outlined below and in Appendix A and Appendix B:

Table 12: Vital Sign Measurements

	Screening	Day 1 of all Cycles (Predose) ^a	Every 30 Minutes During IMGN853 Infusion ^{b,d}	Following Completion of IMGN853 Infusion ^c	4-hours Post End of Infusion ^d	At Same Time as ECG Assessments	End of Study and FUP Visits
Blood Pressure	•	•	•	•	•	•	•
Pulse	•	•	•	•	•	•	•
Respiratory Rate	•	•	•	•	•	•	•
Temperature	•	•	•	•	•		•

^a Within 10 minutes prior to start of infusion

8.7. Electrocardiogram (ECG)

A standard, single 12-lead electrocardiogram (ECG) will be performed within 14 days prior to first dose to determine study eligibility.

On study ECGs will be performed in triplicate at the following timepoints in Cycles 1 and 3:

- Baseline ECG: Within one hour prior to the first dose
- Post Dose ECGs:
 - \circ End-of-infusion to coincide with C_{max} and PK blood draw (within one hour from this blood draw)
 - \circ 24 ± 2 hours post infusion to coincide with PK blood draw

Triplicate ECGs will be performed at 2-5 minute intervals. A single ECG will also be performed at the end of treatment visit and as clinically indicated (Appendix A and Appendix B).

Vital signs (blood pressure, pulse, and respiratory rate) will be measured within 10 minutes of completion of each set of triplicate ECG readings.

ImmunoGen, Inc. Confidential Page 86 of 138

 $^{^{\}rm b}$ \pm 10 minutes

^c Within 10 minutes following completion of infusion

^d Cycles 1 and 2 only. If the patient's infusion was well-tolerated, the 4-hour post infusion assessment will not be required in Cycles ≥3.

^e Measured predose and within 10 minutes of completion of each set of triplicate ECG readings (predose, end of infusion to coincide with C_{max} PK draw (+10 minute window) and 24 hrs post infusion (±2 hours) – See also Section 8.7.

8.8. Pulse Oximetry

Pulse oximetry will be performed prior to dosing on Day 1 of every cycle and as indicated in Section 10 (Study Activities) and Appendix A and Appendix B (Schedule of Clinical Assessments for Schedules A and B, respectively).

8.9. Pulmonary Function Tests

Pulmonary function tests (PFTs) should include spirometry, diffusion capacity, and lung volume tests. PFTs will be performed within two weeks prior to Cycle 1 Dayl and in the event of pulmonary symptoms as clinically indicated (Appendix A).

8.10. Laboratory Assessments

Patients should be in a seated or supine position during blood collection. Screening labs (hematology, clinical chemistry, and urinalysis) may be performed within 14 days of first dose. Repeat testing on Cycle 1, Day 1 is not required if tests were obtained within 4 days of dosing and are within acceptable ranges. Repeat testing will be performed as outlined in the Schedule of Clinical Assessments (Appendix A and Appendix B) and as clinically indicated.

Note that prior to each administration of IMGN853, laboratory results must be reviewed to evaluate for potential toxicity.

8.10.1. Clinical Laboratory Panels

Table 13: Clinical Laboratory Tests

Hematology	Serum Chemistry	Coagulation Tests	Urinalysis	Other
 Hematocrit Hemoglobin WBC (w/5-part differential) RBC Platelet count 	 Albumin Alkaline phosphatase ALT AST BUN Calcium Carbon dioxide Chloride Creatinine Glucose LDH Magnesium Phosphorus Potassium Sodium Total bilirubin 	PTaPTTINR	 pH Ketones Protein Glucose Occult blood Leukocyte esterase Nitrite (microscopic examination of sediment will be performed only if results of urinalysis dipstick are positive) 	β-hcG homocysteine methylmalonate

WBC, white blood cell count; RBC, red blood cell count; ALT, alanine aminotransferase; AST, aspartate aminotransferase; BUN, blood urea nitrogen; LDH, lactic acid dehydrogenase; GFR, glomerular filtration rate; INR, International Normalized Ratio; PT, Prothrombin time; aPTT, Activated partial thromboplastin time

ImmunoGen, Inc. Confidential Page 87 of 138

8.11. Pregnancy Screen

All female patients of child-bearing potential will complete a serum beta-human chorionic gonadotropin (β -hCG) or urine pregnancy test (not more than 3 days before the first dose of IMGN853); this test must be negative for the patient to be enrolled and to receive the study drug.

If a female patient becomes pregnant or suspects pregnancy while participating in this study, the Investigator and Sponsor must be informed immediately and the patient will be withdrawn from study treatment.

8.12. Eastern Cooperative Oncology Group Performance Status

Eastern Cooperative Oncology Group (ECOG) performance status (Appendix D) will be assessed during screening and at other times specified in the Schedule of Clinical Assessments (Appendix A and Appendix B). An assessment is not necessary on Day 1 of Cycle 1 if the screening assessment was obtained within 3 days prior to Day 1.

8.13. Radiologic Imaging

Radiographic tumor evaluation by computed tomography (CT) or MRI of chest, abdomen, and pelvis (EOC patients only) will be performed within 28 days prior to first dose and approximately every second cycle, from the date of first dose until the 28-day Follow-up visit. The same radiographic assessment used at screening must be used at all subsequent radiographic evaluations.

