8.14. Tumor Response Assessment

Tumor response for patients with measurable lesions should be assessed using RECIST 1.1 (Eisenhauer 2009, Appendix E). Patients with ovarian and uterine cancer will have CA125 measured at approximately the same time they undergo radiologic assessment. Patients will have a baseline tumor assessment done within the 28 days prior to Cycle 1, Day 1. Patients with measurable lesions should be assessed using CT scan approximately every second cycle, from the date of first dose until the 28-day Follow-up visit. Although progression may be determined by the investigator based upon clinical deterioration, every effort should be made to document progression using radiographic methods. The basis for determination of progression per clinical deterioration should be documented.

Patients experiencing CA125 response must have a confirmatory test performed at least 28 days after initial response is documented. In the case of stable disease (SD), follow-up measurements must have met the SD criteria at least once after study entry at a minimum interval of 6 weeks.

Electronic copies of radiologic images with tumor size measurements, including baselines assessment, must be sent to the sponsor within 4 weeks after PR/CR has been documented, together with a copy of the corresponding radiology report and tumor assessment worksheets. Scans must be in Digital Imaging and Communications in Medicine (DICOM) format. Electronic transfer of scan files (via FTP, HTTP, or similar means) is preferred, although transfer on physical media (such as DVD or CD) is acceptable. For digital media, one time point/patient/disk is expected. The site is expected to maintain a copy of digital data for the retention period applicable to the protocol, Good Clinical Practices (GCP), and federal, international, and/or state legal and medical requirements. ImmunoGen will retain the media for

ImmunoGen, Inc. Confidential Page 88 of 138

a period of 2 years following the date a marketing application is approved or, if no application is to be filed or if the application is not approved for such indication, until 2 years after the investigation is discontinued.

Note: It is very important that the same method of radiologic assessment be used throughout the study and that the same lesions are followed.

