10.5. Even-Numbered Cycles (2, 4, 6, etc.), End of Cycle

- Pregnancy test (may be performed more frequently in accordance to institutional requirements) (Appendix A and Appendix B)
 - o **Schedule A** − Day 18±3 days
 - Schedule B Day 21±3 days
- For patients who experience ocular toxicity and those who experience blurred vision but have normal eye examinations: complete ophthalmic examination (Section 5.8.8); to be performed by a board-certified ophthalmologist prior to the start of every other cycle from the time it is first reported.
- Tumor assessments by CT scan (Appendix A and Appendix B)
 - **Schedule A** Every 6 weeks±1 week

- o **Schedule B** − Every 8 weeks±1 week
- CA125 for patients with EOC, primary peritoneal cancer, fallopian tube cancer or uterine cancer (Appendix F) should be scheduled to coincide approximately with the radiographic tumor assessments

NOTE: Patients experiencing CA125 response must have a confirmatory test performed 28 days after initial response is documented.

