- i. Radiographic tumor assessment by CT scan is to be performed every 6 weeks (± 1 week). Additionally, patients with elevated CA125 at baseline will have CA125 measured at approximately the same time they undergo radiologic assessment. Patients experiencing CA125 response must have a confirmatory test performed at least 28 days after initial response is documented.

ImmunoGen, Inc. Confidential Page 122 of 138

- j. If a patient discontinues prior to documentation of PD, a tumor assessment is to be performed at the End of Study visit or 28-Day Follow up visit, if not performed within the previous 6 weeks. Tumor assessments will be performed every 12 weeks until progression is documented or the patient begins a new treatment regimen. Patients who have discontinued study treatment for reasons other than PD will be followed per RECIST 1.1 (Appendix E) every 12 weeks (±3 weeks) until documentation of PD, starting a subsequent anti-cancer therapy or for up to one year from Cycle 1, Day 1, whichever comes first.
- k. ECGs will be performed as outlined in Section 8.7.
- 1. As clinically indicated.
- m. Only AEs and SAEs attributed to study procedures are recorded.

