- d. Vital signs (blood pressure, pulse, respiration rate, and temperature) will be measured as outlined in Section 8.6 and 8.7.
- e. Day 1 laboratory assessments may be performed up to 4 days prior to study agent administration. Laboratory results must be reviewed prior to each scheduled administration of IMGN853. In the event of severe toxicity, repeat laboratory tests should be performed as necessary until the toxicity resolves or stabilizes. For a complete list of laboratory assessments, refer to Section 8.10.
- f. For WCBP, a urine or serum pregnancy test will be performed at screening, prior to dosing on Day 1, every-other-cycle while on study and at the 28-day Follow-Up visit. Additional testing may be performed in accordance with institutional requirements or local regulation.
- g. Baseline ophthalmic exams will be performed by a board-certified ophthalmologist and will include the following: indirect fundoscopy, slit lamp examination under dilatation, intraocular pressure measurement, and corneal photography. A Schirmer test will be performed at baseline for all patients, and for patients who experience ocular symptoms, it will be repeated at the first on-study ophthalmic examination and at subsequently if clinically indicated. May be performed within 14 days of Cycle 1, Day 1. Ocular symptom assessment will be performed prior to the start of each cycle by the treating physician or other qualified individual. If the subject reports ocular symptoms then IMGN853 will be stopped and the subject will then be referred to an ophthalmologist for a complete examination (Section 5.8.8). Patients who experience ocular toxicity will have a complete ophthalmologic exam performed every other cycle, including patients with blurred vision but normal eye examinations. All patients will have a complete ophthalmologic exam performed at the End of Treatment visit or 28-Day Follow Up.
- h. Radiographic tumor assessment by CT scan is to be performed every 8 weeks (± 1 week). Additionally, patients with elevated CA125 at baseline will have CA125 measured at approximately the same time they undergo radiologic assessment. Patients experiencing CA125 response must have a confirmatory test performed at least 28 days after initial response is documented.

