- there has been prior documented progression in the lesion by at least 2 sequential CT or MRI scans performed after the completion of radiation, or
- histopathological evidence of progression

Additionally, if such lesions meet the criteria for measurability, they may be considered target lesions.

Imaging Methods

The same method of assessment and the same technique used to characterize each identified and reported lesion at baseline should be used during each follow-up assessment. Imaging-based evaluation is preferred to evaluation by clinical examination unless the lesion(s) being followed

ImmunoGen, Inc. Confidential Page 131 of 138

cannot be imaged but are assessable by clinical exam (referring to biopsy-proven visible lesions(s) at the vaginal apex).

Chest X-ray: Lesions that are identified on chest X-ray must be confirmed and followed by CT scan. If there is/are pre-existing chest lesion(s) before the baseline tumor assessment, a chest X-ray is not necessary to assess those lesions. The pre-existing chest lesion(s) must be assessed at baseline and followed by CT scans.

Conventional CT or MRI: This guideline has defined measurability of lesions on CT scan based on the assumption that CT slice thickness is 5 mm or less. If CT scans have slice thickness greater than 5 mm, the minimum size for a measurable lesion is twice the slice thickness. MRI is also acceptable in certain situations (e.g., for body scan) except for lung.

CA-125: Tumor marker CA125 alone cannot be used to assess response or determine progression; however, it will be followed. CA125 measurements should be scheduled to approximately coincide with radiological assessment (every 6 weeks ± 1 week). Patients whose CA125 is above the upper normal limit at baseline will need to have their values normalize to \leq upper normal limit, in addition to complete disappearance of measurable or evaluable disease, in order to be considered in complete response.

Other methods of assessment, PET-CT, ultrasound and FDG-PET should not be used for response assessment in this study.

Time Point Assessments

Patients will have tumor measurements performed within 28 days prior to baseline and every 6 weeks thereafter (± 1 week).

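### Protocol 8.13 and 8.14 tie tumor scans to treatment cycles while 10.5 and the appendices give calendar weeks; once dosing is delayed the rules diverge and progression may be dated late

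*Protocol*

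**What the plan says.** Two kinds of scan rule stand in the current protocol text.

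- **By cycle.** Section 8.13 asks for imaging "approximately every second cycle, from the date of first dose until the 28-day Follow-up visit". Section 8.14 says measurable disease "should be assessed using CT scan approximately every second cycle".
- **By calendar.** Appendix A, footnote i (Schedule A): "Radiographic tumor assessment by CT scan is to be performed every 6 weeks (± 1 week". Appendix B, footnote h (Schedule B): "Radiographic tumor assessment by CT scan is to be performed every 8 weeks (± 1 week".
- **Mixed.** Section 10.5 gives the same calendar figures (for Schedule A, "Every 6 weeks±1 week"), but under the heading "Even-Numbered Cycles (2, 4, 6, etc.), End of Cycle". The grids are laid out the same way: the scan sits in the Cycle 2 Day 18±3 column in Appendix A and in the Day 21±3 column in Appendix B.
- **One interval for all.** Appendix E says "every 6 weeks thereafter (± 1 week" without excepting Schedule B.

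SAP 5.1.3 and 5.1.5 date progression for PFS and TTP from radiology as judged by the investigator, and clinical progression does not count. SAP 5.1.1 sets a 35-day minimum for stable disease, which it derives as 6 weeks less a 1-week window.

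**The concern.** The two rules coincide only while dosing stays on time, and the protocol expects that it sometimes will not. Section 5.8.8 holds treatment for ocular symptoms of Grade 2 or higher. Section 5.9.1.1 allows a toxicity delay of up to 21 days before removal from treatment, and longer in patients with clinical benefit.

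A site that follows 8.13, 8.14 or the 10.5 heading may wait for the delayed cycle to end before scanning. A site that follows the appendix footnotes will not. Apart from deaths in PFS, the event date in PFS and TTP is a scan date. Under the cycle reading, the timing of assessment would therefore depend on how much toxicity a patient had and on how the site read the protocol. DOR ends at the same progression date, although its start is also a scan date, so its net shift is not determined.

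**Working it through.** **Inputs.** Cycle length is 21 days (A) and 28 days (B). Calendar interval is 42 days (A, window 35 to 49) and 56 days (B, window 49 to 63), from 10.5 and Appendices A and B. Toxicity delay is up to 21 days per cycle (5.9.1.1). The SAP censors a progression when the gap since the last scan, plus 1, is at least 105 days (5.1.3). The documents give no expected PFS median, so true medians of 3 to 8 months are an assumption.

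**1. No delay.** 2 × 21 = 42 days and 2 × 28 = 56 days, so the rules agree. The SAP's stable-disease figure also reproduces: 6 × 7 − 7 = 35 days.

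**2. With delay, cycle reading.** Interval = 2 × cycle length + total delay in the block.

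| Delay in block | Schedule A (35–49) | Schedule B (49–63) |
|---|---|---|
| 7 days, one cycle | 49 | 63 |
| 14 days, one cycle | 56 | 70 |
| 21 days, one cycle | 63 | 77 |
| 14 days, both cycles | 70 | 84 |
| 21 days, both cycles | 84 | 98 |

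A total delay of up to 7 days stays inside the window. Every larger delay in the table falls outside it.

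**3. First scan.** In the Appendix A grid it falls at Cycle 2 Day 18±3, before Cycle 3 starts, so only the delay to the start of Cycle 2 can precede it. With a 14-day delay Cycle 2 starts on study day 22 + 14 = 36, and its Days 15 to 21 are study days 50 to 56. With a 21-day delay they are study days 57 to 63. The 70- and 84-day intervals can arise only in later blocks.

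**4. SAP gap rule.** The longest interval in the table gives 98 + 1 = 99, below 105. Such a progression is kept as a later event and is not censored.

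**5. Mean lag in detecting progression.** For scans every T days and exponential true progression times with rate λ = ln 2 / median, mean lag = T / (1 − exp(−λT)) − 1/λ. Schedule A:

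| T (days) | Lag, 3-month median | Excess over 42 | Lag, 8-month median | Excess over 42 |
|---|---|---|---|---|
| 42 | 22.1 | 0 | 21.4 | 0 |
| 56 | 30.0 | 7.9 | 28.7 | 7.3 |
| 63 | 34.0 | 11.9 | 32.4 | 11.0 |
| 84 | 46.4 | 24.3 | 43.7 | 22.3 |

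One 14- to 21-day delay in every scan interval therefore costs about 7 to 12 days on average. The 84-day row applies only if every cycle slips 21 days.

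**6. Observed median.** A simulation used exponential times, scans jittered uniformly by ±7 days, true medians of 3, 4 and 6 months, 25% to 100% of patients delayed, and 14, 21 or 42 extra days per two cycles. The median shifted by −13.7 to +40.6 days. It moves in steps because progressions are recorded at scan dates. For example, a 6-month true median is 6 × 30.4375 = 182.6 days. The next 42-day scan after that is nominally day 210, but the next 63-day scan is day 189, so the observed median falls. With a 4-month median and everyone delayed, 14 extra days moves it by +32.1 days and 21 extra days by only +0.4.

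**The case against.** The strongest reply is that a calendar rule with an explicit window is already written, in 10.5 and Appendices A, B and E. Sections 8.13 and 8.14 can be read as a summary: they say the interval is approximate and they count from first dose. The SAP's 35-day rule matches the 6-week calendar. Sites that follow the appendix footnotes would show no shift from on-treatment delays. All of that stands, and it makes the effect conditional. It does not remove the conflict, because no passage gives the appendices precedence and the calendar figures are themselves filed under cycle headings and columns.

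Three stronger inferences are tempting and are not supported.

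- A reader might take the first scan to slip from week 6 to week 10 or 12. The Appendix A layout allows only one delay before it.
- A reader might take progression dates to be 4 to 6 weeks late in each block. That is the worst case of a single interval with both cycles delayed 14 or 21 days. It does not accumulate, because the lag is bounded by the one interval in which progression occurs.
- A reader might use the 50% blurred-vision rate in Protocol 11.1 to conclude that delays will be common. That figure is an ungraded planning rate for an adverse event, not a rate of dose delay.

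The stakes are also limited. The trial is non-randomized, tests no formal hypothesis and has MTD and RP2D as its primary endpoints. Schedule B is closed to new patients, so the 6- versus 8-week conflict in Appendix E concerns only those continuing on it.

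**Conclusion.** The inconsistency is real and should be resolved. It is moderate in weight. Where sites follow the cycle wording, scans in patients with toxicity holds may fall outside the intended window, and progression will then be detected later on average, by the amounts in step 5. Those amounts rest on exponential progression times, the assumed medians, and a delay recurring in every scan interval.

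A reader might conclude that PFS in this trial lengthens with toxicity. The documents support only that it may. The effect depends on site practice, which they do not describe. It holds for the mean lag and not reliably for the reported median, which is the statistic the SAP tabulates.

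**What to change.** - **8.13 and 8.14:** replace the two-cycle phrase with 'every 6 weeks ±1 week (Schedule A) or every 8 weeks ±1 week (Schedule B), counted from Cycle 1 Day 1 and not shifted for dose delays'.
- **10.5 and the Appendix A and B grids:** keep the calendar weeks, add 'counted from Cycle 1 Day 1, not shifted for dose delays', and take the scan out from under the even-numbered-cycle heading or column.
- **Appendix E:** limit the 6-week text to Schedule A.

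The Schedule A interval then stays at 42 days (35 to 49) whatever the on-treatment delay, and the excess lag from that source is zero. The change is wording only and adds no scans beyond those Appendices A and B already require. The cost is that some scans will not coincide with a dosing visit.

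It leaves one separate link with toxicity in place: patients who stop treatment without progression move to scans every 12 weeks ±3 weeks (Protocol 10.8) under either reading.
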